### Blinding

No blinding will be applied in the study.

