## Clinical Research Plan

# Importance of the study

Head posture varies according to the physiologic and functional activity of the individual. Head postures are divided into 'active feeding position', 'head up position', and 'extended head position'. (1,2) The position in which the head extends 30° forward during feeding is known as the 'active feeding position'. (2) This posture causes the mandible and mandibular closure pathways to be positioned more anteriorly than normal. During drinking, the head extends 45° backwards and the mandible moves posteriorly. (3) Any change in head posture causes the muscles attached to the mandible to stretch and lengthen, resulting in a change in mandibular position. Changes in mandibular position result in changes in occlusal contact points and the occlusal forces generated at these points. The literature supports the relationship between head posture and occlusal contact points. (4,5)

Micron-sized changes in occlusal contacts can trigger severe dysfunction and pain in the temporomandibular joint (TMJ). Therefore, it is important to obtain accurate interocclusal records and to detect occlusal interferences. The interocclusal record is defined as a record of the positional relationships of opposing teeth and jaws. (6) Interocclusal records facilitate the assessment of occlusion for diagnostic or treatment planning purposes. Restorations with occlusal incompatibility produced using inaccurate interocclusal records result in increased adjustment time of the restoration or the need for restoration replacement. This is time-consuming and costly for both the clinician and the patient. Therefore, reliable interocclusal records obtained by providing appropriate occlusal records directly affect the success of prosthetic or indirect restorative procedures. (7)

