Investigational products have been manufactured in accordance with good manufacturing practices determined according to the relevant legislation. These products will be used in accordance with the approved research protocol. The control and calibration procedures of the devices to be used within the scope of the research will be carried out regularly. The data obtained will be stored in the software of the devices and will not be shared with third parties. Personal data will not be shared with anyone and will be kept only by the clinician. Data that do not contain personal data, which are shared with the dental laboratory after being created with the coding method, will be automatically deleted from the software used by the dental laboratory within a maximum of three months from the date of sharing. The records of the devices in the system will be deleted immediately after the completion of the work. Confidentiality assurance of the data will be realized with the form signed by the individuals. A comparative device will not be used in the study. In case of early termination or temporary suspension of the study for any reason, the volunteers included in the study will be immediately informed by the principal investigator. The principal investigator or a researcher to be assigned by the principal investigator will immediately notify the sponsor of all adverse events, serious adverse events, device defects. The volunteer experiencing an adverse event will be followed up at the research center until the effects disappear completely and regain their health, and necessary interventions will be made. Information on patient code, age, gender, inclusion and end date will be recorded on the case report form in order to ensure accurate patient follow-up. In case of any damage that may occur to the volunteers due to the research, the damage will be immediately notified to the sponsor and will be provided within the scope of the research. Digital interocclusal records and oJMA records, which are found to be useful within the scope of the research, can also be used in the future prosthetic dental treatment of the volunteers. The results of the study may be used in dental education or scientific publications without disclosing the personal information of the volunteer. If the volunteer signs the 'Informed Voluntary Consent Form', he/she consents to the right of access to the original medical records by monitors, examiners, the Ethics Committee, the Ministry and other relevant health authorities related to this research, but the information is under the assurance of complete confidentiality.

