## oJMA Record

For each participant, the spatial position of the maxilla relative to the skull base, the condyle distance and the static and dynamic recording of the mandible will be taken in accordance with the digital occlusal analysis module in the oJMA.

All records will be completed in two sessions and carried out by a single operator. During the first session, participants will be scanned using the intraoral scanner (TRIOS4; 3Shape A/S; Copenhagen, Denmark) in accordance with the scanning protocol recommended by the manufacturer. Each of the scans will take 1.5 minutes and will be completed in a total of three minutes. A goniometer (Goniometer, 360°; Saehan, Germany) will be used to standardize the head position of participants before taking interocclusal records in the dental unit. (13,14) All participants will be in the dental unit, where the back of the unit will support the person's lumbar and thoracic vertebrae, with their arms freely sitting next to the body and watching directly in front of them. The neutral position of the head (G1, PN), 30° flexion (G2, PF), and 45° extension (G3, PB) will be determined by a goniometer. For each participant, the neutral position will first be determined, with the head, neck, and spine on the same axis, the fixed arm of the gonyometer standing on the ground, the central meatus acusticus externus, and the measuring arm aligned with the Camper plane. Then, for

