each head position, the measuring arm shall be fixed to the base of the ala nares, with the head in the position of 30° flexion and 45° extension. Then, in addition to normal clinical procedures, these two head positions will take right and left direct digital interocclusal records. These records will take one minute for each main position, and inter-occlusal records will be completed in a total of three minutes. The closing movement will be repeated to get the participants to an intercuspal jaw position, and the muscles will get used to this position. Subsequently, participants will be asked to close their mandible in a repeated intercuspal position and they will be asked to maintain this position. The intraoral scanner will be placed between the teeth and the cheek with minimum pressure, without disturbing the closure, and will be recorded from the teeth's buccal surfaces with movement from the rear to the front. The TRIOS software will automatically match the same areas in the dental arch scans during the interocclusal record with the scan of the buccal surface of the teeth, closing the scans of the lower and upper jaws. Participants will repeat the same procedure for right and left interocclusal records without disturbing the intercuspal jaw position. The oJMA will be recorded at the second session and last 15 minutes. All recordings will then be integrated into the analytical module of the oJMA software (zebris WINJAW+; zebris Medical GmbH, Germany) in 'stl' format.

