# Sample size and strength analysis

This study uses the PS Version 3.0 package. =0,50,  $\alpha$ =0,05, test strength 1-=080, repetition correlation r=0,20 is the default, and the total sample size is determined to be at least 36. But because working with a larger sample reduces the level of misunderstanding, it is desirable to work with as many patients as possible.

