### **Primary Data**

The primary data for each participant will be collected in the 'stl' format obtained by scans of the participant's maxillary and mandibular archs and interocclusal records, obtaining three different head positions. These data will also be matched using software (zebris WINJAW+; zebris Medical GmbH, Germany), and the differences between the interocclusal contacts will be quantified.

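### The no-blinding rule also covers the later file-based contact quantification, which could be masked cheaply if it needs operator choices

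*Combined protocol and SAP*

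**What the plan says.** The Blinding section is one sentence: "No blinding will be applied in the study". It does not separate recording from later processing.

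Under Primary Conclusion Point, the endpoint is a quantitative comparison of interocclusal contacts across the head positions. Two places show where those values come from. The oJMA Record section says, after describing both sessions, "All recordings will then be integrated into the analytical module of the oJMA software", in stl format. Primary Data says "These data will also be matched using software (zebris WINJAW+; zebris Medical GmbH, Germany), and the differences between the interocclusal contacts will be quantified".

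Three other statements bear on the point:

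- On who takes the records (oJMA Record): "All records will be completed in two sessions and carried out by a single operator".
- On automation (oJMA Record): "The TRIOS software will automatically match the same areas in the dental arch scans during the interocclusal record".
- On file coding (Materials and Methods), the confidentiality text refers to "Data that do not contain personal data, which are shared with the dental laboratory after being created with the coding method".

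**The concern.** Each participant supplies a record in all three positions, so the result is a within-person contrast between positions. Suppose the person who quantifies the contacts makes judgements and knows which file is neutral, flexion or extension. A systematic tendency in those judgements would then enter the contrast directly. It could not be separated from a true effect of posture afterwards, because it would be aligned with position in every participant.

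The analyst may also hold an expectation. Importance of the study says of the forward feeding posture: "This posture causes the mandible and mandibular closure pathways to be positioned more anteriorly than normal". It then describes the mandible moving the other way when the head is tilted back to drink. The plan's formal hypothesis is no difference, but its background gives a direction for each posture.

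The blanket rule gives up protection at a stage where protection would be possible and probably cheap.

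**Working it through.** There is no figure in the plan to reproduce on this point, so the check sets the relevant sections side by side.

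1. **Where the endpoint arises.** Primary Conclusion Point defines it as contact differences between positions. Primary Data and the end of oJMA Record place the quantification in WINJAW+, on stl files, after recording. It is a separate, later step.

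2. **Can recording be masked?** Not realistically. Under oJMA Record, the head is set to neutral, 30° flexion or 45° extension with a goniometer before the interocclusal records are taken, and a single operator takes all records. That operator must know the position.

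3. **Can the file step be masked?** In principle, yes. The input is a set of files, and a file can carry a code in place of a position label. The plan does not show whether the module can process records under codes. Primary Data speaks of quantifying differences, which leaves open that records are compared jointly rather than one at a time.

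4. **Is the file step automatic?** The documents do not say. The one step described as automatic is the TRIOS matching of the buccal scan to the arch scans, which happens in the scanner software before export. For WINJAW+ the plan gives no contact threshold, alignment setting or rule for which contacts count, and does not name who runs it. Statistical Evaluation covers tests only and does not fill this gap.

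5. **Does existing coding already mask the files?** No. The coding in Materials and Methods appears in the text on personal data and laboratory sharing. It is not said to hide head position or to apply to the analyst.

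6. **Scale of the task.** Sample size and strength analysis states "repetition correlation r=0,20 is the default, and the total sample size is determined to be at least 36". Materials and Methods and Randomization each count three records per participant. At the minimum sample: 36 participants × 3 positions = 108 position records. The number rises with the sample, which the plan allows to be larger.

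7. **Size of any bias.** It cannot be derived. The documents give no reading error, no repeatability of contact quantification and no estimate of a shift between masked and unmasked readings.

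**The case against.** The strongest reply is that the mechanism depends on a fact the documents do not give. Nothing in the plan describes an operator choice in WINJAW+. It says that the data are matched by software and the differences quantified. If that runs without input under one set of settings, knowledge of head position cannot alter the values and masking gains almost nothing. This stands, and it is why the point is conditional.

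A second reply is that fixing the settings concerns how the endpoint is defined, not blinding. That is partly right: unstated settings would be a gap even in a masked study. But fixed settings applied equally to all positions also remove the discretion through which knowledge of position could act, so the sentence belongs here as well.

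A third reply is that the gain is limited. Jaw displacement visible in the aligned scans may reveal the position, and coding does nothing about the single unmasked operator or the non-randomised records. This also stands. It limits the benefit but does not remove it.

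A reader might infer something stronger: that the primary endpoint is biased, or that its false-positive rate is inflated by a known amount. The documents support neither. Any rate would need an assumed shift and an assumed test, since Statistical Evaluation leaves the test open, and the same rate would follow from any other source of bias. It would not be evidence about unmasked quantification.

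**Conclusion.** The point holds as a low-cost improvement to consider. The Blinding section, as worded, covers the file-based step that yields the primary endpoint, and the plan does not show that this step is free of operator judgement. No size can be put on the possible bias. It could be nil.

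The conclusion rests on two things that the documents leave open: whether WINJAW+ quantification needs operator input, and whether the module can handle coded records. If the step is fully automatic, only the request for fixed settings remains. The absence of blinding at recording is not criticised here, since masking the operator is not practicable in this design.

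**What to change.** Before finalising, the investigator should confirm whether WINJAW+ contact quantification is automatic, who performs it, and whether the module can process coded records. Then replace the Blinding text with:

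> Recording is unblinded. WINJAW+ settings for contact quantification are fixed before any file is analysed and applied identically to all positions. Where quantification needs operator input, record files carry random position codes that keep the participant link, are processed in random order, and are decoded only after contact values are locked; the key is held by an existing team member other than the analyst.

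If the step proves fully automatic, keep only the first two sentences. The cost is then writing down the settings.

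Otherwise the cost is a small coding task, about 108 position records at 36 participants, and a key holder from the existing team. Sample size, sessions and head positions do not change. If the module cannot work with coded records, the measurement procedure would have to change and the cost would be higher; that should be settled before the text is adopted. The plan should also state that masking may be incomplete, because jaw displacement can reveal position, and that it does not protect against bias arising at recording.

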### **Primary Data**

The primary data for each participant will be collected in the 'stl' format obtained by scans of the participant's maxillary and mandibular archs and interocclusal records, obtaining three different head positions. These data will also be matched using software (zebris WINJAW+; zebris Medical GmbH, Germany), and the differences between the interocclusal contacts will be quantified.

# **Primary Conclusion Point**

The comparison of the interocclusal records obtained is a quantitative evaluation of differences in interoclusal contacts in different head positions according to the appropriate head-bone-spine position.

#### **Statistical Evaluation**

Data from all volunteers participating in the study will be included in the statistical analysis. First, the Kolmogorov Smirnov adaptation test and the Shapiro-Wilk test are considered to be used to see if the data has a normal distribution. Subsequently, the differences between groups will be assessed using parametric or non-parametric statistical methods, depending on the case. Previous studies will be studied in detail, and comparisons will be evaluated using appropriate tests. Taking into account previous studies, it is envisaged that independent and dependent group tests, Kruskal Wallis, or one-way variance analysis, will be used.

Any possible change in the clinical research plan or process will be promptly notified to the research center, relevant institutions, boards, and healthy volunteers. Derogations from the clinical research plan are monitored and managed by the research center, and inconsistencies with the plan are expressly prohibited.

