#### **Randomization:**

The study was planned as a clinical trial. The planned digital interocclusional recordings for three different head positions will be completed in a single session, and the recording groups will not change. The total of three different records to be taken will not be subject to randomization in itself.

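### The method is chosen by two normality tests on an unspecified scale, with no rule for when they disagree; one paired primary analysis should be fixed in advance

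*Combined protocol and SAP*

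**What the plan says.** The Statistical Evaluation section is the whole analysis plan. It opens with the normality check: "the Kolmogorov Smirnov adaptation test and the Shapiro-Wilk test are considered to be used to see if the data has a normal distribution". It continues: "the differences between groups will be assessed using parametric or non-parametric statistical methods, depending on the case". For the tests themselves, "it is envisaged that independent and dependent group tests, Kruskal Wallis, or one-way variance analysis, will be used". It gives no significance level for the normality tests, no rule if they disagree, no version of the Kolmogorov-Smirnov test (with or without the Lilliefors correction), no definition of the data being checked and no single primary test.

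Two other sections bear on the scale. Under Randomization, "The planned digital interocclusional recordings for three different head positions will be completed in a single session", so each volunteer supplies all three values. Under Primary Data, "the differences between the interocclusal contacts will be quantified". The Primary Conclusion Point asks for a "quantitative evaluation of differences in interoclusal contacts in different head positions".

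**The concern.** With three values per person, a paired t-test or a repeated-measures ANOVA relies on the distribution of the within-person differences or residuals. The spread between people does not enter. A few volunteers with much larger contacts make each position's raw values look skewed, but they cancel when positions are subtracted. A normality test on raw values can therefore reject for a reason that has no bearing on the paired analysis, and send the study to a rank test it does not need.

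The gate itself is also undefined. Two tests with different sensitivity are named and neither takes precedence. When they disagree, the analyst has two defensible routes to the primary p-value and can see both results before choosing. The rank route also answers a different question: Friedman compares ranks within a person, whereas the primary endpoint asks how large the difference is.

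**Working it through.** **Inputs from the plan.** At least 36 volunteers, three positions each, alpha 0.05, power 0.80, a standardised effect of 0.50 and r = 0.20 (Sample size and strength analysis: "This study uses the PS Version 3.0 package. =0,50" and "test strength 1-=080, repetition correlation r=0,20 is the default"). The symbol before 0.50 was lost in text extraction, so its scale is not known here. Two-sided testing is assumed.

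**The plan's own figure.** If 0.50 is in SDs of the within-person difference, a two-sided paired t-test (noncentral t) needs 34 volunteers and has 83.1% power at 36. That is close to the stated 36 but makes no use of r. If 0.50 is in SDs of the raw values, the difference has SD √(2 × (1 − 0.20)) = √1.6 = 1.265. The effect is then 0.50 / 1.265 = 0.395, and 53 volunteers are needed. The sample-size text therefore does not settle which analysis is primary.

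**Assumed inputs.** The documents give no distribution for the contact measure and no correlation other than 0.20. The simulations use 36 people and three positions. Setting A has a log-normal person effect (log-SD 0.75), normal errors and an effect set for about 80% power with repeated-measures ANOVA. Setting B has means 0, 0.25 and 0.5 raw-value SDs and, where skewed, a log-normal person effect with log-SD 1.

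**Step 1: how often the raw-value gate rejects.** Shapiro-Wilk at 5% on each position, any rejection counted, skewed person effect and normal errors:

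| | Raw values | Differences from neutral |
|---|---|---|
| r = 0.20 | 25% | about 10–11% |
| r = 0.6 | 63% (A), 67% (B) | about 8–10% |

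**Step 2: cost when Friedman is the fallback.** Its asymptotic efficiency against repeated-measures ANOVA for normal errors and three positions is (3/π) × 3/(3 + 1) = 0.955 × 0.75 = 0.72. The expected loss is roughly the switching rate times the power gap. In setting A at r = 0.20 this is 0.252 × (80.4 − 65.5) = 3.8 points; direct simulation gives 80.4 − 76.9 = 3.5.

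| Skewed person effect | ANOVA fixed | Switch to Friedman | Loss |
|---|---|---|---|
| A, r = 0.20 | 80.4% | 76.9% | 3.5 |
| A, r = 0.6 | 80.2% | 72.6% | 7.6 |
| B, r = 0.20 (either test rejects) | 54.2% | 50.8% | 3.4 |
| B, r = 0.6 (either test rejects) | 84.9% | 75.0% | 9.9 |

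With fully normal data the loss is 2 to 3 points in setting B (53.8% to 51.8%; 85.5% to 82.9%) and 1 to 2 in setting A.

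**Step 3: cost when the signed-rank test is the fallback.** In setting B with a skewed person effect, paired t against signed-rank is 64.8% against 62.5% at r = 0.20 and 89.6% against 89.2% at r = 0.6. Multiplying by the switching rate gives 0.248 × 2.3 = 0.6 and 0.669 × 0.4 = 0.3 points.

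**Step 4: skewed measurements.** With log-normal measurements (log-SD 0.5) and an additive effect, switching gains power over raw-scale ANOVA: 55.4% to 61.1% at r = 0.20 and 82.3% to 89.8% at r = 0.6. With log-SD 0.75 and a multiplicative effect, raw-scale ANOVA has 62–66%, the switch 66–68%, and ANOVA on a log scale stated in advance 79–81%.

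**Step 5: disagreement between the two tests.** At n = 36 the 5% critical value of the Kolmogorov-Smirnov statistic is 0.221 uncorrected and 0.146 with Lilliefors correction. Disagreement with Shapiro-Wilk in at least one position:

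| | Lilliefors | Uncorrected |
|---|---|---|
| Normal data | 15–16% | 13–14% |
| Skewed person effect | 19–22% | 24–57% |

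**Step 6: null rejection.** A fixed two-stage rule stays near nominal, at 4.7–6.0%. Taking the favourable result whenever the two tests disagree gives 5–7%.

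**The case against.** Four points can be made for the plan.

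- A reader might infer that the plan tests raw values instead of within-person differences. It never says so. Primary Data speaks of quantifying differences, and the Primary Conclusion Point is framed relative to the appropriate posture, so the data checked may already be differences. This stands: the fault is an unspecified scale, not a demonstrated wrong one. The raw-value reading remains the more natural, because the positions are labelled as groups and Kruskal-Wallis and one-way ANOVA are normally applied to values per group. If differences are meant, saying so is part of the same edit.
- A reader might infer that power is lost in general. That does not hold either. The losses in Step 2 assume normal errors, which favours ANOVA, and Step 4 shows the direction reverses against raw-scale ANOVA when the measurements themselves are skewed. What remains is that a scale chosen beforehand does better than the switch in that case too.
- The simulated rule is not the plan's. Friedman and repeated-measures ANOVA are not named there, only unspecified dependent-group tests, and the 0.72 efficiency applies to Friedman alone. This is fair, and is why the loss is stated separately by fallback.
- The independent-group tests listed in the same section cost more: one-way ANOVA has 43% power against 54% for repeated-measures ANOVA at r = 0.20, and 35% against 86% at r = 0.6 (normal data, setting B). True, but removing them would still leave an undefined gate between the paired alternatives.

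**Conclusion.** The point holds in limited form. The plan lets two normality tests select the method without saying what they are applied to or which prevails, although the design is fully paired. The conditional power cost is about 3 points at the plan's r = 0.20 and about 8 at an assumed r = 0.6, given raw-value testing, a skewed person effect, normal errors and Friedman as fallback. It is near zero with the signed-rank test, and absent against raw-scale ANOVA when the measurements are skewed.

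The open choice does not depend on those distributional assumptions: about 13–16% disagreement even with normal data, whichever version of Kolmogorov-Smirnov is used. A reader might infer a serious type I error problem. The figures do not support that: a fixed rule stays near 5%, and even selective use reaches only about 7%. Priority is minor to moderate, and the point is best corrected together with the independent-group tests in the same section.

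**What to change.** In Statistical Evaluation, remove the normality tests as the selector and state:

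1. The primary analysis, used whatever the distribution looks like, is the within-person contrasts flexion minus neutral and extension minus neutral. Each is reported as a mean difference with a 95% interval, from a paired t-test or from a repeated-measures model with unstructured covariance.
2. Shape is examined only on these differences or the model residuals, by plot.
3. The contact measure is named. If it is expected to be skewed in proportion to its size, such as an area, the log scale is declared before any data are seen.
4. A signed-rank or bootstrap result is a named sensitivity analysis and does not replace the primary one.

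If both contrasts are primary, the text should also say how the 5% is shared. An equal split needs 41 volunteers for 80% power at 0.50 SDs of the difference, against 34 for a single contrast.

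The drafting cost is a few sentences. The downside is that a mean-based primary result is kept even if the differences prove skewed on the chosen scale; the sensitivity analysis then shows how much that matters.

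### The named tests compare only the location of the contact measure between head positions and no within-person change is reported, so a non-significant result would not show that individual records are unchanged

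*Combined protocol and SAP*

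**What the plan says.** All places are in the combined protocol and SAP.

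- **Statistical Evaluation** puts normality tests first, after which "the differences between groups will be assessed using parametric or non-parametric statistical methods, depending on the case". The methods it envisages are independent- and dependent-group tests, Kruskal-Wallis and one-way analysis of variance. The final choice is left open.
- **Digital Interocclusal Record Groups** and **Materials And Methods** show that the groups are three head positions (neutral, 30° flexion, 45° extension) recorded in the same volunteers.
- **Primary Conclusion Point** calls the endpoint a "quantitative evaluation of differences in interoclusal contacts in different head positions", judged against the appropriate alignment. **Primary Data** adds that the records are matched in software and the differences quantified. Neither section gives a unit, or says whether the result is a count, area or distance, signed or unsigned.
- **Importance of the study** sets the hypothesis as no statistically significant difference between postures. Its background says: "Restorations with occlusal incompatibility produced using inaccurate interocclusal records result in increased adjustment time of the restoration or the need for restoration replacement".
- **oJMA Record** describes interocclusal recording at each position but no repeat recording in neutral.
- **Sample size and strength analysis** assumes that "repetition correlation r=0,20 is the default" and concludes that "the total sample size is determined to be at least 36".

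No section plans a summary of how much each volunteer's record changes.

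**The concern.** The study hypothesis is one of no difference, so a non-significant result is a likely headline. It would be natural to read it as saying that head position leaves the interocclusal record alone. That is a statement about individual records, and a restoration is made from one person's record.

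A location test cannot support it. If some volunteers gain contacts and others lose them when the head is tilted, the location can stay put while individual records move. Choosing a paired test does not cure this, because it still tests the mean or location of the differences. A confidence interval for the mean difference also describes the average only. The within-person differences that would show the spread are available by subtraction from the planned records, but the plan does not ask for them.

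**Working it through.** **Inputs.** From Sample size and strength analysis: effect 0.50 (its symbol was lost when the text was read), alpha 0.05, power 0.80, correlation r = 0.20, n = 36. From Materials And Methods: three records per volunteer. Assumed here: a signed, roughly normal measure with SD 1 at each position, and two-sided tests.

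**The plan's own figure.**
- Reading 0.50 as the standardized mean of the paired differences, the normal approximation gives n = (1.960 + 0.842)² / 0.50² = 31.4, so 32. The noncentral t gives 34, close to 36, and power at 36 is 0.831. This reading does not use r.
- Reading 0.50 as a difference in SD units with r = 0.20 gives 53.
- A repeated-measures F test with f = 0.50 and r = 0.20 gives 12 volunteers, which is 36 records.

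The sample size does not decide the present point. It supplies r and n.

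**Step 1: why location tests can miss it.** Let a share p of volunteers shift by +D and the rest by −D in one position.
- Mean difference = (2p − 1)D. This is 0 at p = 0.5, D/2 at p = 0.75 and D at p = 1.
- Variance of the within-person differences ≈ 2(1 − r) + 4p(1 − p)D².
- With r = 0.20 and no shift, SD = √1.6 = 1.265. With p = 0.5 and D = 2, SD ≈ √(1.6 + 4) = 2.37.

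The mean stays at zero and the spread nearly doubles. The spread carries the information, and the plan does not report it.

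**Step 2: size of the effect.** Rejection rates in 4,000 simulated trials of 36 volunteers at r = 0.20, with one position shifted. The range is over paired t, repeated-measures F, one-way ANOVA, Kruskal-Wallis and Friedman tests.

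| Shift D (SD) | Half up, half down | 75% up, 25% down | All up |
|---|---|---|---|
| 0.5 | 1.8–4.1% | 12–19% | 54–68% |
| 1 | 0.6–2.4% | 42–51% | 98.7–99.8% |
| 2 | 0–0.2% | 90–100% | 100% |

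Masking is near complete only when directions are balanced. At a 75/25 split it is partial, and it has largely gone at 2 SD.

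**Step 3: what 36 volunteers could report.**
- SD of a difference = √(2(1 − r)).
- 95% limits of agreement around the mean difference = ±1.96 × SD.
- Standard error of a limit = SD × √(1/36 + 1.96²/(2 × 35)) = 0.2875 × SD. The 95% half-width is 2.03 times that (t, 35 df).
- 95% half-width for the mean difference = 2.03 × SD / √36.

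| r | SD of difference | Limits | Half-width, each limit | Half-width, mean |
|---|---|---|---|---|
| 0.2 | 1.265 | ±2.48 | ±0.74 | ±0.43 |
| 0.5 | 1.000 | ±1.96 | ±0.58 | ±0.34 |
| 0.8 | 0.632 | ±1.24 | ±0.37 | ±0.21 |

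All are in SD units. The r = 0.5 and 0.8 rows are assumptions, shown for range. These limits arise with no posture effect at all: they follow from r.

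**The case against.** **The group test answers the stated hypothesis.** The aim is to compare contacts across three positions, the sentence on inaccurate records is general background, and no section says that a null result will be taken to mean unchanged individual records. This stands. The group test is valid for its own question. What remains is the limit on what a null result can claim, and the plan does not state it.

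**The rationale is direction-specific.** Importance of the study has the mandible moving forward in one posture and backward in the other, and eligibility is restricted to Angle Class I without joint dysfunction. A balanced split is therefore less likely. This stands for jaw position. The rationale does not say whether contacts are gained or lost.

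**The measure may be unsigned.** Primary Data could mean an absolute deviation from each volunteer's own neutral record, and such deviations cannot cancel. This stands, so the point is conditional.

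**Stronger readings that the documents do not support.**
- A reader might infer that the plan compares only group averages. The text does not say so: Kruskal-Wallis uses ranks, dependent tests use within-person differences, and the choice is open.
- A reader might compute that at r = 0.20 and zero mean change, 69% of volunteers would differ from neutral by more than 0.50 SD (0.50/1.265 = 0.395; two-sided normal tail 0.69), and conclude that most records change with posture. Two neutral records with r = 0.20 would give the same 69%. Nor is 0.50 a threshold for a materially changed record; it is a planning effect size.

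**Limits of agreement cannot isolate posture.** With no repeat neutral record, they mix posture with closing and scanning variation, and the plan has no acceptance margin. This stands and shapes the fix.

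**Conclusion.** The point holds in conditional form. Every named method tests location, no within-person summary of change is planned, and a non-significant result would therefore not show that individual records are unchanged.

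How much could be hidden depends on two things the documents leave open: whether the measure is signed or a count, and how evenly individual changes divide. Under the assumptions above, a 1 SD shift is detected in at most 2.4% of trials if evenly divided, in about half or fewer at 75/25, and almost always if uniform. The documents give no data on the direction or size of individual changes, so no share of volunteers affected by posture can be derived. If the measure is an unsigned deviation from neutral, the cancellation argument falls away.

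This does not invalidate the planned comparison. It is a gap in reporting and interpretation that is cheap to close before analysis.

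**What to change.** In Statistical Evaluation, alongside the group comparison:

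1. For flexion minus neutral and extension minus neutral, report the mean within-person difference with its 95% confidence interval, the SD of the differences, and the 95% limits of agreement with their confidence intervals. Use percentile limits if the differences are skewed. Plot the individual differences.
2. State that a non-significant group test alone will not be reported as showing that head position leaves the contacts unchanged.
3. State that the limits describe total record-to-record change, including closing and scanning variation, so wide limits cannot be attributed to posture.
4. Require that any statement of unchanged contacts rest on a margin set before analysis.
5. State in Primary Data and Primary Conclusion Point whether the measure is signed, a count or an unsigned deviation. If it is an unsigned deviation from neutral, report its distribution (median and an upper percentile) in place of item 1.

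The cost is a few lines of text, one table and one plot from records already planned, with no new volunteers, visits or measurements. The price is that the limits may be wide and the conclusion less favourable. Separating posture from measurement variation would need repeat neutral records, which this change does not supply.
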